1.1 Scope of document

The SAP (Statistical Analysis Plan) documents contain detailed information to aid the production of Statistics & Programming input into the Clinical Study Report (CSR) for trial “CLFG316X2202”.

The SAP describes the implementation of the statistical analysis planned following study termination which is reduced in scope compared to the original protocol. Objectives and other text remain as in the protocol.

1.2 Study reference documentation

This SAP has been developed using Clinical Trial Protocol version v05 (incorporating Amendment 05) dated 16 AUG 2016.

1.3 Study objectives

1.3.1 Primary Objective

To assess the hematological response rate in patients with TAM receiving LFG316 compared to standard of care (SoC).

1.3.2 Secondary Objectives

- To assess the safety and tolerability of LFG316 in patients with TAM
- To describe the pharmacokinetics of total LFG316
- To evaluate non-relapse mortality in TAM patients treated with LFG316 as compared to patients on SoC
- To assess complete response rate at 17 weeks in TAM patients treated with LFG316 compared to patients receiving standard of care

1.3.3 Exploratory Objectives

[figure not shown]
Corporate Confidential Information

1.4 Study design and treatment

This is a randomized, SoC-controlled, open-label, multi-center study in patients with TAM after hematopoietic precursor cell transplantation (HPCT) from a related or unrelated donor for malignant and nonmalignant disease after myeloablative or non-myeloablative conditioning.

The study will consist of up to 28 days of screening period, 16 weeks treatment period that can be extended to 45 weeks (in case of ongoing symptoms of TAM), 36 weeks follow up, and end of study visit (EOS) at week 52 (Figure 1-1). Duration of follow up will depend on duration of treatment. Patients who are treated for more than 41 weeks will proceed directly to EOS visit.

Figure 1-1

Approximately 40 patients were to be randomized to receive SoC alone or LFG316 plus SoC (excluding plasmapheresis and prohibited treatment). Patients would be included in the study if they have diagnosis of TAM and poor prognostic markers. Corporate Confidential Information

Patients randomized to LFG316 received [redacted] on study days 1, 8, and 15, followed by weekly doses of [redacted] for remaining treatment duration of total 16 weeks.

Patients showing worsening disease (definition below) after two weeks of treatment (day 15) or later until visit at week 3, will be considered failures and could be switched to receive the alternative treatment (SoC or LFG316).

- increasing schistocyte count (+50% or more as compared to baseline),

- and/or increase in erythrocyte or platelet transfusion need (increase of 50% or more in number of transfusions during 2 weeks prior to study visit as compared to number of transfusions needed two weeks before treatment initiation),
- and/or increasing proteinuria (+50% or more as compared to baseline)

Patients showing no response (definition below) between visit at week 4 (day 29) and visit at week 16 were considered to be treatment failures and could be switched to the other treatment arm. Switching the treatment could occur immediately after data is available.

- no decrease in schistocyte count (as compared to baseline)
- and/or continued erythrocyte or platelet transfusion need (less than 25% improvement in number of transfusions during 2 weeks prior to study visit as compared to number of transfusions needed two weeks before treatment initiation)
- and/or non-responding proteinuria (less than 25% reduction in proteinuria compared to baseline)

Patients can only switch study treatment arms once.

2 First interpretable results (FIR)

First interpretable results (FIR) will not be provided for this trial.

3 Interim analyses

Corporate Confidential Information

4 Statistical methods: Analysis sets

For patients for which the actual first treatment received does not match the randomized treatment then the treatment actually first received will be used for grouping by treatments received.

All patients who receive study drug or SoC and with no protocol deviations with relevant impact on safety will be included in the safety analysis set.

The PK analysis set will include all patients with at least one available valid (i.e. not flagged for exclusion) PK concentration measurement, who received study drug or SoC and who experienced no protocol deviations with relevant impact on PK data.

Corporate Confidential Information

Patients who switch treatments according to the protocol defined rules will be indicated as having received two treatments in the listings, and data from the period after switching will in general be summarized separately if required. Thus in general there may be up to 6 treatment groups in the summary tables:

- LFG316
- SoC
- LFG316 then SoC (in case of switch in treatment)
- SoC then LFG316 (in case of switch in treatment)
- All LFG316 first
- All SoC first

with the first four, mutually exclusive, used in listings, 'by treatment'.

The analysis sets and protocol deviation codes are related as follows:

Table 4-1 Protocol deviation codes and analysis sets

Category Deviation code	Text description of deviation	Data exclusion
Patients are excluded from all (safety) analysis in case of these PDs:		Exclude patient completely from all (safety) analysis sets
I01	ICF not obtained	
Patients are excluded from PK analysis in case of these Protocol Deviations:		Exclude patient from PK analysis set
E11	Patients previously treated with eculizumab for TAM	Unless sufficiently long ago to not affect PK.
Patients are excluded from PD analysis in case of these Protocol Deviations:		Exclude patient from PD analysis set
E01	Use of other investigational drugs at the time of enrollment, or within 5 half-lives of enrollment, or until the expected PD effect has returned to baseline, whichever is longer; or even longer if required by local regulations. Investigational drug does not include off label use of drugs. Non-marketed drugs used in expanded access programs that are used as local standard of care may be acceptable but have to be agreed with the sponsor on a case by case basis.	

Category Deviation code	Text description of deviation	Data exclusion
E11	Patients previously treated with eculizumab for TAM	Unless sufficiently long ago to not affect PD.

If updates to this table are needed, an amendment to the SAP needs to be implemented prior to DBL.

5 Statistical methods for pharmacokinetic (PK) parameters

5.1 Variables

The following pharmacokinetic parameters will be determined (if feasible) using non-compartmental method(s) with Phoenix WinNonlin (Version 6.2 or higher): AUC(0-tlast), AUC(0-t), Cmax, tmax, Cmax/D, AUC/D. The linear trapezoidal rule will be used for AUC calculation.

5.2 Descriptive analyses

Total LFG316 serum concentration data will be listed by treatment (excluding patients receiving SoC alone), patient, and visit/sampling time point. Descriptive summary statistics will be provided by drug treatment and visit/sampling time point, including the frequency (n, %) of concentrations below the LLOQ and reported as zero.

Summary statistics will include mean (arithmetic and geometric), SD, CV (arithmetic and geometric), median, minimum and maximum. An exception to this is Tmax where median, minimum and maximum will be presented. Concentrations below LLOQ will be treated as zero in summary statistics and for PK parameter calculations. A geometric mean will not be reported if the dataset includes zero values. Pharmacokinetic parameters will be listed by treatment and patient.

5.2.1 Graphical presentation of results

Arithmetic mean (SD) and geometric mean (95% CI) serum concentration data will be plotted across time up to a timepoint where there is sufficient data for calculation of means

Overlaying individual serum concentration-time profiles will be generated along with concentration versus time profiles for individual patients.

6 Statistical methods for Efficacy and Pharmacodynamic (PD) parameters

Summary of key estimands for efficacy

Efficacy estimands are defined for this trial to address the efficacy objectives of the trial and to provide supportive evidence for those objectives. These estimands are defined in detail in the subsequent sections and are summarized in Table 6-1. Although they will be calculated for each patient and treatment they will not be analysed, only listed. The outputs for safety, tolerability, PK, PD and PK/PD relationships are described in other sections of this SAP.

Table 6-1 Summary of key protocol estimands

	Estimand	Variable estimand is based on	Section
P1	Primary	Hematological response at 17 weeks on initially randomized treatment	6.1.1
S1	Secondary - non-relapse mortality	Non-relapse death or switching up to 17 weeks	6.2.1
S2	Secondary - complete response	Complete response at 17 weeks on initially randomized treatment	6.3.1
S3	Secondary for overall survival	All cause death over one year	6.4.1

6.1 Primary estimand

The primary estimand addresses the primary objective:

- To assess the hematological response rate in patients with transplant associated microangiopathy (TAM) receiving LFG316 plus standard of care (SoC) (excluding prohibited treatment) against SoC only.

This estimand addresses the scientific question of whether treatment with LFG316 only increases hematological response rate compared to treatment with SoC only. It is assumed that treatment switching implies that the randomized treatment has failed and that the patient is deteriorating.

6.1.1 Definition of primary estimand: Hematological response (P1)

- Population: TAM patients with high risk of death as per the inclusion/exclusion criteria
- Variable: Hematological response at 17 weeks
- Measure of intervention effect: Difference between response rates for LFG316 versus SoC in the absence of a switch to alternative treatment (considered failure)

A patient is considered to have hematological response at a given timepoint if both of the following criteria are met:

1. Schistocytes <2/microscopic high power field (HPF).
2. Transfusion independent (no need for TAM-related transfusions [platelets and erythrocytes])

Patients meeting the definition of hematological response at week 17 whilst still remaining on their randomized treatment are considered to be responders.

Therefore patients who switch treatments before week 17 are considered to be non-responders.

Patients who do not meet the responder criteria and have missing data are also considered to be non-responders.

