6.5 Other exploratory secondary variables

The following variables will also be listed and plotted over time to support the assessment of efficacy as they are components of hematological response (first three) and of complete response (all five).

- Schistocytes
- Platelets
- Erythrocytes
- Proteinuria
- eGFR

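### Does counting every switcher, and every patient without week-17 data, as a non-responder need changing in the primary listing?

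*SAP*

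**What the plan says.** Under Section 6.1.1 a responder has fewer than 2 schistocytes per high power field, needs no TAM-related transfusions, and is still on the randomized treatment at week 17. Two rules follow. On switching: "Therefore patients who switch treatments before week 17 are considered to be non-responders". On missing data: "Patients who do not meet the responder criteria and have missing data are also considered to be non-responders".

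Section 6.1 gives the reasoning for the first rule: "It is assumed that treatment switching implies that the randomized treatment has failed and that the patient is deteriorating".

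Section 1.4 sets out when a switch is allowed. From day 15 to week 3 the patient must be worsening, and each of the three criteria needs a rise of at least 50%. After that the test is different: "Patients showing no response (definition below) between visit at week 4 (day 29) and visit at week 16 were considered to be treatment failures". The three later criteria begin with "no decrease in schistocyte count (as compared to baseline", continue with less than 25% improvement in transfusions, and end with "and/or non-responding proteinuria (less than 25% reduction in proteinuria compared to baseline".

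Section 6.5 lists schistocytes, platelets, erythrocytes, proteinuria and eGFR, and describes them as "components of hematological response (first three) and of complete response (all five". Proteinuria is fourth in that list.

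Section 1.1 gives the setting: "The SAP describes the implementation of the statistical analysis planned following study termination". It adds that objectives and the remaining text are carried over from the protocol. Section 6 states that the efficacy estimands are derived for each patient but only listed.

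**The concern.** Two things look wrong on a first reading.

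First, the stated reason for the switch rule does not match the switch criteria. A patient who is stable, or improving slightly, can switch between week 4 and week 16 without deteriorating. Because the criteria are alternatives, the switch can rest on proteinuria alone, and proteinuria plays no part in hematological response. Such a patient could have met both hematological criteria at the time of the switch and still be listed as a hematological non-responder.

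Second, the plan was written with the termination known, yet it keeps the rule that missing data mean non-response. A patient whose week-17 visit never took place because the study stopped would carry the same label as a patient whose treatment failed.

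At stake is how the patient-level primary listing is read. No summary of the primary variable is planned, and the visible text names no column giving the reason for non-response.

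**Working it through.** The SAP states no figure for this point, so there is none to reproduce. The check compares the sections and tests whether the awkward cases can arise.

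**1. Which criteria require worsening (Section 1.4)**

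| Window | Criteria | Require worsening | Concern proteinuria |
|---|---|---|---|
| Day 15 to week 3 | 3 | 3 | 1 |
| Week 4 to week 16 | 3 | 0 | 1 |
| Total | 6 | 3 | 2 |

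**2. Length of the windows.** Section 1.4 equates week 4 with day 29, so day = 7 × week + 1. Week 3 is then day 22 and week 16 is day 113.

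- Early window: (22 − 15)/7 = 1 week.
- Late window: (113 − 29)/7 = 12 weeks.
- Late share: 12/(1 + 12) = 92%.

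This is a share of calendar time, not of switches or patients. The late criteria also admit patients who are worsening: a rising schistocyte count is not a decrease, and a rise in transfusions or proteinuria is less than a 25% improvement. So in those 12 weeks deterioration is not guaranteed, but it is not excluded either.

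**3. Can a hematological responder be allowed to switch?** Take two hypothetical patients (values assumed). In both, schistocytes go from 6 to 1 per field and transfusions from 4 to 0, so both meet the two response criteria.

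- Patient A: proteinuria goes from 100 to 80. The reduction is (100 − 80)/100 = 20%, below 25%, so the late rule is met on proteinuria alone. No early criterion is met.
- Patient B: proteinuria goes from 100 to 150. The rise is (150 − 100)/100 = 50%, so the early rule is met on proteinuria alone.

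Three alternative criteria give 2³ − 1 = 7 non-empty combinations, and proteinuria alone is one of them. The case is possible. The SAP does not say whether it occurred.

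**4. Does the switch rule depend on the deterioration sentence?** In Section 6.1.1 the rule follows from the requirement to be on randomized treatment at week 17. The effect measure there also declares a switch to be a failure. Section 1.4 treats switchers as failures in both windows, which agrees with the first half of the Section 6.1 assumption. If the second half is deleted, patients A and B, once switched, are still non-responders. The number of patients whose status changes is 0.

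**5. What the reader can see elsewhere**

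- Section 4: listings use four mutually exclusive treatment sequences, so switchers are set apart.
- Section 6.5: the response components and proteinuria are listed and plotted over time.
- Section 7.1.2: drug administration is listed, laboratory plots change colour at a switch, and transfusions are listed by visit.

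The course before a switch and an absent week-17 value can be read from these. An explicit statement of the switch criterion, or of why week 17 is missing, is not among the outputs described.

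**6. Effect on a result.** If a response rate were computed, relabelling one patient would move it by 1/n: 5.0 points at n = 20 per arm, within a range of 10.0 (n = 10) to 3.3 (n = 30). Arm sizes are assumed, because the SAP gives only a planned total of about 40 and no allocation ratio. No such rate is planned, so the effect on planned results is nil.

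**The case for a change.** The best case for a change is this. Because the primary variable is only listed, the label is in effect the primary result, with no summary or sensitivity analysis behind it. A plan written after termination could foresee a week-17 visit lost for administrative reasons and should settle it. The remedy looks cheap: one reworded sentence, a column for the reason, and a category for patients who could not be evaluated.

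Part of this stands. The Section 6.1 wording is broader than the week 4 to week 16 criteria allow. A reason column would also save a reader from checking several listings.

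The rest does not carry a change. If a switch is accepted as failure, a patient who switched on proteinuria alone is labelled correctly under the declared composite, and the remaining request concerns listing layout. The SAP sets out no complete column layout for any listing, and parts of it are redacted, so an unnamed column is a detail left to the analysts. A not-evaluable category is more than layout: it would redefine the primary variable of an open-label trial after termination, when Section 1.1 carries that text over from the protocol. The termination argument also reaches only patients stopped before week 17. Someone who met the criteria at week 17 on randomized treatment and was stopped later remains a responder.

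**Conclusion.** No change to the plan is called for. The mismatch between Sections 6.1 and 1.4 is real but clerical, since the switch rule stands on the responder definition and the composite without the disputed words. The missing reason for non-response is a gap that analysts can largely fill from the treatment-sequence, component and transfusion listings, and they may add a reason column without altering the definition. Counting missing data as non-response is a conventional choice that Section 1.1 openly retains.

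The size is nil for any planned rate, comparison or conclusion. The number of patients with a label that could mislead cannot be stated from the SAP and may be zero.

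This rests on two conditions: that the primary variable stays listed and unanalysed, as Section 6 says, and that the component and transfusion listings are produced as described. If a response rate were later reported, the make-up of the non-responder group would matter and should be shown beside it.

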6.2 Secondary estimands for non-relapse mortality

This secondary estimand addresses the following secondary objective:

- To evaluate non-relapse-related mortality (any death not considered to be related to a relapse of underlying disease) in TAM patients treated with LFG316 as compared to patients on SoC

6.2.1 Definition of secondary estimand for non-relapse mortality:

- Population: TAM patients with high risk of death as per the inclusion/exclusion criteria
- Variable: Time to non-relapse-related mortality up to 17 weeks on initially randomized treatment.

6.3 Secondary estimand for complete response:

6.3.1 Definition of secondary estimand for complete response:

- Population: TAM patients with high risk of death as per the inclusion/exclusion criteria
- Variable: Complete response at 17 weeks

Complete response is defined as hematological response and no proteinuria as determined by proteinuria <30 mg/dL and eGFR doubled or not less than 0.85 x lower limit of normal

6.4 Secondary estimand for overall survival

6.4.1 Definition of secondary estimand for overall survival (S3):

- Population: TAM patients with high risk of death as per the inclusion/exclusion criteria
- Variable: Time to all cause death up to 1 year on initially randomized treatment.

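### Does the unexplained treatment qualifier in the overall survival definition (S3) leave the handling of a treatment switch open in a way that matters?

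*SAP*

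**What the plan says.** Four estimands are summarized in SAP Table 6-1 (Section 6) and defined in Sections 6.1 to 6.4. The S3 row of the table reads "All cause death over one year". Section 6.4.1 gives a population and one further line, "Variable: Time to all cause death up to 1 year on initially randomized treatment", and stops there. It has no sentence on switching.

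The other rows deal with treatment more openly. P1 is "Hematological response at 17 weeks on initially randomized treatment" and S2 is "Complete response at 17 weeks on initially randomized treatment". S1 is "Non-relapse death or switching up to 17 weeks", so a switch is part of that variable, although Section 6.2.1 describes S1 with the same qualifier as S3 and does not mention switching. For P1, Section 6.1.1 spells the idea out: patients who meet the criteria at week 17 "whilst still remaining on their randomized treatment are considered to be responders", and those who switch earlier are non-responders.

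Two general statements also bear on S3. The introduction to Section 6 says that the estimands are derived per patient and treatment but are only listed, not analysed. Section 4 says that switchers "will be indicated as having received two treatments in the listings", and that "data from the period after switching will in general be summarized separately if required". It then names four mutually exclusive groups for listings, two of which are the switch sequences.

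**The concern.** The qualifier in Section 6.4.1 is missing from the S3 row of Table 6-1, although the table carries it for P1 and S2. Elsewhere in the SAP it tends to go with a rule under which a switch changes the outcome: failure for P1, and part of the variable in the Table 6-1 row for S1. A programmer who follows that pattern could end S3 at the switch or count the switch as an event. One who follows the S3 row of the table would count every death within the year.

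Switching is built into the design (Section 1.4), from day 15 up to the week 16 visit, while S3 runs for a year. Most of a switcher's year therefore falls after the switch. If S3 were compared between arms, the choice would matter: dropping deaths after a switch would remove events from patients whose first treatment had failed, and the censoring would be informative. That is why the wording deserves a look.

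**Working it through.** The SAP gives no sample size, event count, switch rate or mortality rate for S3, so there is no figure to reproduce. The check compares the texts and follows one patient through the possible readings.

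**Step 1: candidate readings of Section 6.4.1.**
- (a) By randomized arm: every death up to 1 year counts under the arm first assigned.
- (b) Until switch: follow-up ends at the switch, and a later death is not an S3 event.
- (c) Composite: the switch is itself an event, as in the Table 6-1 row for S1.

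**Step 2: one switcher.** Count from study day 1, with a switch at day 29, which is (29 − 1)/7 = 4 weeks, and death in week 30.

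| Reading | S3 time | S3 status |
|---|---|---|
| (a) | week 30 | event |
| (b) | week 4 | no event |
| (c) | week 4 | event |

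The times differ by 30 − 4 = 26 weeks, and the status differs between (b) and the other two. For a patient who never switches, the three readings give the same entry.

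**Step 3: how much of the year is exposed.** The exposed part is 52 − w weeks, where w is the week of the switch. At day 15 (w = 2) it is 50 weeks; at week 16 it is 36 weeks. These are calendar windows that any one-year endpoint would have. They do not measure an effect. An entry is affected only if the patient switched, and the number of such patients is not in the SAP.

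**Step 4: does the SAP favour a reading?**
- The introduction to Section 6 says that the later sections define the estimands in detail and that Table 6-1 summarizes them. A shorter phrase in the table is therefore an abbreviation. The table also leaves out that S1 and S3 are times to an event.
- Under (a), Section 6.4.1 and Table 6-1 say the same thing.
- A strict on-treatment meaning fits a one-year horizon poorly. Treatment lasts 16 weeks, extendable to 45 (Section 1.4), so an unswitched patient would spend 52 − 16 = 36 weeks, or at least 52 − 45 = 7 weeks, outside it.
- Reading (c) draws some support from Section 6.2.1, where S1 has the same qualifier and its table row counts switching. But the S3 row does not mention switching, whereas the S1 row does.
- No passage says that a death after a switch is dropped.

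**Step 5: could such a death appear only under the second treatment?** The statement in Section 4 on separate presentation after a switch concerns summaries, and S3 has none. The listing groups in Section 4 are sequences, so a switcher's death appears under that patient's sequence.

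**Step 6: what uses S3?** Only a listing. The SAP plans no survival curve, hazard ratio, test or S3 summary table. Overall survival is also not among the secondary objectives in Section 1.3.2.

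**The case for a change.** The strongest case for a change is that the listing is the only planned presentation of S3, so its time and event flag should have one meaning. Someone has to derive them for each switcher, the SAP describes the variable twice in different words, and one added sentence would settle it at almost no cost. The same phrase is loose in Section 6.2.1, where the gap between text and table is plainer, since only the table mentions switching.

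Much of this stands. The wordings do differ, no S3-specific switch rule is given, and (b) and (c) cannot be excluded from the text alone. What does not stand is that the plan contradicts itself or that a result is at risk. A summary row that omits a qualifier is compatible with the detailed definition under the most natural reading. The listing identifies every switcher, so a reader knows which entries need care. The SAP also states that objectives and other text remain as in the protocol (Section 1.1), which may define overall survival and its censoring more fully.

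**Conclusion.** No change to the plan is needed. The wording of S3 is loose, and so is that of S1 in Section 6.2.1, but this is an editorial matter that analysts can resolve sensibly: all deaths up to 1 year, shown by initially randomized arm, with the switch visible in the treatment sequence. That reading agrees with both Section 6.4.1 and Table 6-1.

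The effect is confined to the listed time and event flag of patients who switched. In the worked example that is up to 26 weeks and a reversed event status for one entry. The number of such entries is unknown and may be zero. No estimate, test or conclusion changes under any reading.

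This rests on two conditions stated in the SAP: the estimands stay listed only, and the listings show the treatment sequence. If S3 were later to be estimated or compared between arms, the handling of a switch would have to be fixed first.
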